7.2 REPORTING

All procedures conducted as part of this study are standard procedures in routine care and/or clinical research. In the unlikely event that an AE occurs during a study ENTO2UK Protocol v.1.4 11/06/2018

visit, the relationship of the event to the conduct of the study will be assessed by the PI at site. Only AEs which are determined to have resulted (definitely, probably or possibly) from participation in the study will be recorded as AEs in the study records.

All treatments used in this study are standard treatments or licensed over-the-counter products (i.e. Enterosgel®). Throughout the study the patients will be asked about any unusual symptoms or side effects. The PI will review all such events to establish the potential relationship with use of study treatments. AEs which are determined to be definitely, probably or possibly related to the use of Enterosgel® will be recorded as ADEs in the study records.

All SAE/SADE/UADEs need to be reported to the Sponsor within one working day of the site team becoming aware of them.

8 STATISTICS

8.1 POWER CALCULATION

The power calculation for this study is based on demonstrating superiority of the Interventional Group on the primary outcome, duration (days) of diarrhoea. Power was calculated using an online power calculator for continuous outcome superiority trial (Sealed Envelope Ltd. 2012. Available from: https://www.sealedenvelope.com/power/continuous-superiority/).

In line with some previous studies, we assumed a standard deviation for the duration of diarrhoea of 1.3 days (14,15). In order to detect an average decrease of 1 day in the duration of diarrhoea in the Interventional group compared with the Control group, 36 patients in each group are required for 90% power to demonstrate superiority at 5% significance level. Accounting for a combined patient withdrawal and missing data rate of 30%, 52 patients will need to be randomised into each group. Therefore, the total number of patients enrolled will be 104.

8.2 STATISTICAL ANALYSES

A CONSORT flow diagram will show the progress through the parallel randomised trial (that is, enrollment, intervention allocation, follow-up, and data analysis). The baseline characteristics of the groups will be summarised as mean (standard deviation) or n (%). The baseline characteristics will not be compared statistically, in line with CONSORT.

Primary analysis will be conducted on an intention-to-treat basis. The primary outcome will be summarised as mean (standard deviation). The Interventional

group and Control group will be compared using a t-test or Mann Whitney test, as appropriate. A generalised linear model will undertaken to control for an potentially confounding variables, e.g. age and gender.

Secondary outcomes will be summarised as mean (standard deviation) or n(%) median (interquartile range). The Interventional group and Control group will be compared using a t-test or Mann Whitney test for continuous data (e.g. duration of nausea, vomiting and fever) and chi-square tests for categorical data (e.g. complication rate).

A p-value of <0.05 will be considered to indicate statistical significance and all analyses will be undertaken on STATA.

A 30% drop out has been taken into account in the sample size calculation for the primary analysis to allow for missing data. The extent and reasons for missing data will be reported and investigated to see whether the data is missing at random. This will inform which methods to handle missing data will be employed. Sensitivity analyses will be performed as appropriate.

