3.2 STUDY OUTCOMES

3.2.1 Primary Outcome

Duration of diarrhoea defined as time (hours) from randomisation to first nonwatery stool (soft or firm)

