3.2.2 Secondary Outcome(s)

 Duration of diarrhoea defined as time (hours) from randomisation to last watery stool

Stop Enterosgel if diarrhoea resolved

- 2. Percentage of patients with diarrhoea resolved on Day 3 (i.e. first soft or firm stool recorded on Day 0-3)
- 3. Stool frequency defined as average number of stools/day from randomisation to first soft or firm stool
- 4. Tolerance and safety of Enterosgel® (assessed via Adverse Event (AE) reporting from start of treatment until end of Day 7)
- Percentage of patients with diarrhoea-related complications resulting in hospitalisation, Accident & Emergency department visit, nurse/GP home visit or unscheduled visit to the medical practice from randomisation until end of Day 7
- 6. Duration (days) of the following from randomisation:
 - a) Nausea
 - b) Vomiting
 - c) High body temperature defined as ≥38°C
 - d) Abdominal pain

Patient diary is the data source for all efficacy outcomes. Any AEs related to taking study treatment(s) should also be recorded in the patient diary. Any diarrhoea-related complications resulting in hospitalisation, Accident & Emergency department visit, nurse/GP home visit or unscheduled visit to the medical practice, should be reported by the patient during follow-up calls and recorded by the nurse in practice medical notes and the eCRF.

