4.4 WITHDRAWAL CRITERIA

Patients can withdraw consent at any time without providing a reason. No further

data will be collected after a patient withdraws consent or is withdrawn from the study, but data collected before withdrawal can be used.

In case of the following the patient should be withdrawn from the study:

- 1. Refusal to continue the use study treatments
- 2. Significant deterioration of the patient's status
- 3. Serious Adverse Event (SAE)
- 4. Serious adverse reaction
- 5. Changes in diagnosis
- 6. Major protocol violation (affecting patient safety and/or scientific quality of the data)

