The research nurse or GP will then randomise the patient to the intervention group using a computerised randomisation tool. Patients randomised to the Interventional group will be provided with a sufficient amount of Enterosgel® for 5-7 days of treatment and should take Enterosgel® as instructed in the study-specific instructions which will be provided to them (**Appendix A**). Patients randomised to the Control group will not receive any treatment in addition to the standard of care ORS treatment. The details of prescribed ORS treatment and any dietary recommendations will be recorded in the eCRF.

All patients will be provided with a patient diary (**Appendix C**) to record:

- 1. stool times and consistency
- 2. diarrhoea medication use
- 3. other symptoms (fever, nausea, vomiting etc.)
- 4. any AEs

Patients should fill in the patient diary daily from Day 0 until end of Day 7.

Patients will be asked to take a stool sample on the same day at home in a provided clean container. Patients in the Interventional Group should take the stool sample before taking the first Enterosgel® dose. ORS treatment can be started before taking the stool sample. The sample should be taken to the medical practice by the patient or a family member/friend. It will then be delivered to a local laboratory to test for the presence of rotavirus and diarrhoea causing bacteria (i.e.

Campylobacter, Clostridium difficile, Escherichia coli, Salmonella enterica, Shigella), in order to identify the likely cause of the episode. If there is a reason to suspect norovirus infection (i.e. outbreak), this will also be tested for. Patients who have recently travelled abroad will be additionally tested for *Pseudomonas* and *Vibrio cholerae*. A stool sample will only be collected in baseline and the results will be summarised in baseline characteristics.

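### The primary outcome is a time to event that withdrawal can cut short, but section 8.2 fixes a mean and two tests that cannot use an incomplete time

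*Protocol*

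**What the plan says.** Protocol section 3.2.1 gives the primary outcome as "Duration of diarrhoea defined as time (hours) from randomisation to first nonwatery stool (soft or firm"). Two things can end observation before that stool occurs. Section 6.1.1 limits the diary: "Patients should fill in the patient diary daily from Day 0 until end of Day 7". Section 4.4 says that no further "data will be collected after a patient withdraws consent or is withdrawn from the study, but data collected before withdrawal can be used", and its reasons for withdrawal include "Significant deterioration of the patient's status" and refusal of study treatment.

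For the summary, section 8.2 states: "The primary outcome will be summarised as mean (standard deviation"). On the comparison between arms, the same section says that the Interventional "group and Control group will be compared using a t-test or Mann Whitney test, as appropriate". Adjustment for other variables is by an added generalised linear model. The primary analysis is by intention to treat, and section 8.3.1 puts every randomised patient in that population. On missing data, section 8.2 says that the pattern will be examined, that this will decide how it is handled, and that sensitivity analyses will follow.

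Section 8.1 sizes the trial on 36 patients per group and then enlarges it: "Accounting for a combined patient withdrawal and missing data rate of 30%, 52 patients will need to be randomised into each group".

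The first secondary outcome in section 3.2.2 is a second version of duration: "Duration of diarrhoea defined as time (hours) from randomisation to last watery stool".

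**The concern.** A patient who withdraws on Day 2 with watery stools has no observed duration, but is known to have lasted at least until then. That is a right-censored time. A mean, a t-test and a Mann-Whitney test need a value for each patient and cannot use the partial time. Unless a value is invented, the patient leaves the comparison.

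The remaining patients are those whose diarrhoea was seen to resolve, and short durations are more likely to be seen before a patient leaves. The mean among them is therefore too low, and lower still where loss is heavier. If loss differs between arms, the arm with more loss looks faster, even when withdrawal has nothing to do with how long the illness would have lasted. At stake are the type I error of the main test and the meaning of the estimate.

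**Working it through.** **1. The protocol's own figure.** Inputs from section 8.1: SD 1.3 days, difference 1 day, 90% power, 5% significance, 30% loss. Sidedness is not stated; two-sided reproduces the figure.

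- n per group = 2(z₀.₉₇₅ + z₀.₉₀)² × SD² / difference² = 2 × (1.960 + 1.282)² × 1.69 / 1 = 35.5, so 36.
- 36 / (1 − 0.30) = 51.4, so 52 per group and 104 in total.

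The arithmetic holds. It also shows that 52 − 36 = 16 patients per group are not counted on for the comparison of means.

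**2. What a complete-case comparison estimates.** Let T be the duration and C the earlier of withdrawal and end of Day 7. T is seen only if T ≤ C, so the mean among observed patients estimates E[T | T ≤ C]. This lies below E[T] and falls as withdrawal gets heavier. Two arms with the same T but different C differ in this quantity.

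**3. Size under no true effect.** Simulation with 52 per arm, gamma durations with SD 1.3 days, exponential withdrawal independent of duration, a cut at 7 days and 3,000 runs. The Monte Carlo standard error at 5% is √(0.05 × 0.95 / 3000) = 0.4 percentage points. The protocol gives neither a control mean nor loss by arm, so means of 2.5, 3 and 4 days and the loss splits are assumptions. A negative difference favours the device.

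| Loss, Control / Interventional | Mean (days) | Complete-case difference (days) | t-test | Mann-Whitney | Log-rank |
|---|---|---|---|---|---|
| 30% / 30% | 2.5 | 0.00 | 5.1% | 4.9% | 5.3% |
| | 3 | +0.01 | 4.9% | 5.2% | 5.7% |
| | 4 | −0.01 | 5.2% | 4.8% | 5.2% |
| 20% / 40% | 2.5 | −0.17 | 9.5% | 9.0% | 5.7% |
| | 3 | −0.14 | 7.3% | 7.7% | 4.7% |
| | 4 | −0.10 | 5.9% | 6.2% | 4.7% |
| 10% / 50% | 2.5 | −0.34 | 20.8% | 20.4% | 4.8% |
| | 3 | −0.29 | 16.4% | 15.7% | 5.6% |
| | 4 | −0.21 | 10.7% | 10.1% | 5.2% |

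With the split reversed to 40% / 20%, the bias reverses too: about 0.10 to 0.16 day against the device.

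**4. Sensitivity to the dropout model.** With dropout uniform over Days 0-5, mean 4 and SD 1.3, t-test type I error is about 5-6% at 20% / 40% and 7.5-8.7% at 10% / 50%. The inflation is smaller because these are nominal rates: some patients marked to leave resolve first. With SD 2 instead of 1.3, the figure at 10% / 50% is about 11-13%.

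**5. If loss is related to outcome.** Extreme case: the patients lost are those with the longest durations. For a gamma with shape k = (m/1.3)² and scale 1.69/m, the mean of the rest after losing a fraction q is m × F(c; k + 1) / (1 − q). Here c is the (1 − q) quantile, and F(·; k + 1) is the gamma distribution function with shape k + 1 and the same scale. Loss of 20% against 40% gives differences of −0.34, −0.35 and −0.36 day for means of 2.5, 3 and 4: about a third of the 1-day target, with no true effect.

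**6. With a true 1-day effect (same set-up as step 3).** At 20% / 40% loss the complete-case estimate is −1.32, −1.24 and −1.13 days for control means of 2.5, 3 and 4. At 40% / 20% it is about −0.9 day. At 30% / 30%, log-rank power is 92%, 89% and 86%.

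**The case against.** The strongest reply is that the protocol nowhere says that withdrawn patients are dropped. Section 8.3.1 includes everyone randomised, section 4.4 allows data from before withdrawal to be used, and section 8.2 leaves the missing-data method open. A statistical analysis plan not shown here could settle it, and the 36-of-52 figure is a sample-size allowance, not an analysis rule. This stands as far as it goes: a reader might infer that the protocol prescribes a complete-case analysis, and it does not. But the protocol is not silent on the method. It names a summary and two tests that do not fit a censored time, and it leaves the repair to be chosen after the data are seen.

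Four further readings are tempting and are not supported.

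- That heavier loss in the Interventional group is to be expected because only that group can refuse the gel. Both groups are prescribed rehydration solution, the trial is open, and a control patient may also leave. A patient who stops the gel after a first soft stool already has an observed outcome. Unequal loss is plausible, not predicted. The 30% also combines withdrawal with missing data, so not all of it is cut-off follow-up.
- That the end of Day 7 is a large source of censoring. Under the gamma model with SD 1.3, the chance of lasting beyond 7 days is 0.5%, 0.8% and 2.3% for means of 2.5, 3 and 4 days, and 7.3% for a mean of 5. A Mann-Whitney test can also give patients unresolved at a common cut-off the tied highest rank; it fails for earlier withdrawals.
- That leaving the choice of test open does serious harm. With 36 per arm, choosing by a normality test gives a type I error of 5.0-5.4%, and taking the smaller p-value 5.9-6.4%.
- That the first secondary outcome counts early leavers as recovered. The protocol gives no rule for them, so this is a gap to close and not a stated error.

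**Conclusion.** The mismatch is real and stands in the text: a time to event, cut short mainly by withdrawal, is given a summary and tests that cannot use a partial time. Together with the sizing, this implies a comparison of patients seen to recover, which is not the stated intention-to-treat analysis.

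The size depends on something the protocol does not give, namely how loss divides between the arms. Equal loss brings no bias under no effect. Across the two dropout models, with SD 1.3 and assumed means of 2.5 to 4 days, t-test type I error is about 5-10% at 20% / 40% loss and about 7-21% at 10% / 50%. Censoring-aware tests stay near 5% when withdrawal is unrelated to duration. The upper figures need a large imbalance and should not be read as a forecast. This should be fixed; it does not show that the trial's result must be biased.

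**What to change.** For the primary outcome, replace the choice between a t-test and a Mann-Whitney test with a time-to-event analysis of all randomised patients, censored at the last diary entry or the end of Day 7:

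- Kaplan-Meier curves and medians by group;
- one test named in advance. A generalised Wilcoxon test (Peto-Prentice) and the log-rank test both hold the type I error when censoring is non-informative; in simulations the former has more power for a one-day shift;
- the difference in restricted mean hours to Day 7 with a 95% confidence interval as the effect estimate;
- a sensitivity analysis that counts patients withdrawn for deterioration as unresolved to Day 7, because their censoring is informative and the main analysis assumes that it is not.

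For the first secondary outcome, treat the time as censored when no soft or firm stool follows the last recorded watery stool. Section 5.3, which removes users of antidiarrhoeal medication from the analyses, must be reconciled with the inclusion of all randomised patients.

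The cost is wording in the protocol and the analysis plan; no extra data or patients are needed. There are two small prices. The headline becomes a restricted mean or a median instead of a raw mean. If log-rank is chosen, power for a 1-day effect falls slightly below the planned 90% at control means of 3 and 4 days (89% and 86% at 30% loss in each arm), which is a reason to prefer the generalised Wilcoxon test.

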5 INTERVENTIONS AND STUDY DEVICE

5.1 INTERVENTION

Patients in both treatment groups will be prescribed standard of care oral rehydration solution (ORS) treatment.

Patients will be randomised in 1:1 ratio using a computer-based stratified permuted blocks randomisation tool developed by Sealed Envelope Ltd (London, UK) to:

Control Group: will receive a prescription for standard of care ORS treatment **Interventional Group**: will receive a prescription for standard of care ORS treatment together with an intestinal adsorbent, over-the-counter medical device, Enterosgel® (Bioline Products s.r.o, Czech Republic) to be taken according to study-specific dosage instructions provided in **Appendix A** for 5-7 days. Patients will be given 2 tubes of Enterosgel® 225 g and a pack of 10 Enterosgel® sachets to provide a more convenient alternative if the patient is not at home.

Randomisation will be stratified by site identifier.

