6 STUDY SCHEDULE AND PROCEDURES

Patients will complete 1 visit at their GP practice with 7 follow-up phone calls after the visit. The patients will not be invited for visits outside their standard of care regime. The schedule of visits/calls, and the procedures conducted and data collected at each visit/call are presented in **Table 1**. A +/- 2-day deviation is allowed for the Day 7 follow-up call.

Table 1. Schedule of procedures and data collection.

Procedure	Day 0 (Screening Visit)	Days 1- 7 (Follow-up calls)	End of study
Patient screening and consent	Х		
Demographic information and relevant medical history, symptoms and medication	x		
Randomisation	X		
Prescription for ORS (all patients) and provision of Enterosgel® (Interventional group)	Х		
Stool sample	X		
Other symptoms (vomiting, abdominal pain, nausea, fever etc)*	х	х	
Body temperature*		x	
Stool frequency and form*		х	
Medication use*		х	
Adverse Events*	 	x	
Returning of the diaries			х

^{*}Recorded by the patient in a patient diary from Day 0 (after randomisation) until end of Day 7 (**Appendix C**)

6.1.1 Day 0

On the Day 0 appointment, the patient's eligibility to take part in the study will be confirmed by the GP and written informed consent will be obtained by the GP or nurse before any study procedures take place. Screening will include a physical examination by the GP/nurse to ensure the patient is suitable to take part in the study (including measurement of body temperature, pulse and blood pressure).

The following information is then recorded in the eCRF:

- 1. Demographic information (age, gender, ethnicity)
- 2. Relevant medical history:
 - a) date of onset of symptoms (diarrhoea, vomiting, nausea, abdominal pain, fever etc.)
 - b) contact with suspected infection
 - c) details of travel
 - d) details of possible food poisoning
 - e) any antidiarrheal medication taken during the current episode

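### Randomisation is stratified by site, but the stated primary comparison is unadjusted and the added model is framed as control of confounding; naming site and time since onset would bring a small gain in precision

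*Protocol*

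**What the plan says.** Protocol section 5.1 describes allocation as follows: "Patients will be randomised in 1:1 ratio using a computer-based stratified permuted blocks randomisation tool". It then names the only stratification factor: "Randomisation will be stratified by site identifier". Section 4.3 expects about 15 GP practices.

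Section 8.2 compares the two groups on the primary outcome with a t-test or a Mann-Whitney test, neither of which uses site. It then adds a model: "A generalised linear model will undertaken to control for an potentially confounding variables, e.g. age and gender". Age and gender are the only covariates named, and only as examples. The section does not say whether the test or the model decides the primary result.

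The primary outcome (section 3.2.1) runs from randomisation, not from the start of the illness. Section 6.1.1 puts "date of onset of symptoms (diarrhoea, vomiting, nausea, abdominal pain, fever etc" among the items entered in the eCRF at Day 0, but section 8.2 does not use it.

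**The concern.** Three things do not fit together.

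- **Design and analysis differ.** Blocking within site balances the arms within practices. A two-sample test ignores this, so any between-site variation stays in its error term. If practices differ in how long diarrhoea lasts, the standard error is larger than it needs to be.
- **The reason given for adjusting is the wrong one.** Randomisation already deals with systematic confounding by baseline variables. The reasons to adjust in a randomised trial are that a variable was used to stratify, or that it predicts the outcome.
- **A natural candidate is left unnamed.** Patients enter at different points of a self-limiting illness. Section 4.1 asks for three watery stools in the preceding two days, and sections 4.1 and 4.2 set no explicit limit on how long the episode has lasted. Time already ill may therefore predict time remaining.

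At stake is some power in a trial of 104 patients, and clarity about which analysis gives the primary result.

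**Working it through.** **1. The plan's own figure.** Section 8.1 gives the inputs: "detect an average decrease of 1 day in the duration of diarrhoea"; "we assumed a standard deviation for the duration of diarrhoea of 1.3 days"; "36 patients in each group are required for 90% power to demonstrate superiority at 5% significance level". A two-sided test is inferred.

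n per group = 2 × (1.960 + 1.282)² × 1.3² / 1² = 35.5, so 36.

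Allowing for 30% loss: 36 / 0.7 = 51.4, so 52 per group and 104 in total. This agrees with the plan: "Accounting for a combined patient withdrawal and missing data rate of 30%, 52 patients will need to be randomised into each group". The exact noncentral-t power at 36 per group is 89.6%.

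**2. Adjusting for a prognostic covariate.** The documents do not say how much of the variance time since onset explains, so R² is an assumption. Residual SD = 1.3 × √(1 − R²). Noncentrality = 1 / (residual SD × √(2/36)). Each power below uses 70 degrees of freedom; the covariate itself would take one more.

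| Assumed R² | Residual SD (days) | Noncentrality | Power at 36 per group | Equivalent sample, 1/(1 − R²) |
|---|---|---|---|---|
| 0 | 1.300 | 3.26 | 89.6% | 1.00 |
| 0.05 | 1.267 | 3.35 | 91.0% | 1.05 |
| 0.10 | 1.233 | 3.44 | 92.4% | 1.11 |
| 0.20 | 1.163 | 3.65 | 94.9% | 1.25 |

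**3. Using site.** About 104/15 = 6.9 patients per practice are randomised and 72/15 = 4.8 analysed. The documents give neither an ICC nor a block size. The simulation assumed 15 sites, blocks of 4 within site, 104 randomised, a random 72 analysed, total SD 1.3 and an effect of 1 day or none. Runs had 2,500 to 6,000 replicates, some with equal and some with unequal sites. Ranges below span these runs.

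| Assumed ICC | Type I error, t-test | Power, t-test | Power, random site effect | Power, 15 fixed site terms |
|---|---|---|---|---|
| 0 | about 5% | about 90% | about 90% | about 86% |
| 0.05 | 4.6 to 4.7% | about 90% | 91.3 to 91.5% | 87 to 88% |
| 0.10 | 4.4 to 5.0% | 90 to 91% | 91.7 to 91.9% | 89 to 90% |
| 0.20 | 3.6 to 4% | 91 to 92% | 93.4 to 93.9% | about 92 to 93% |

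The t-test's reported standard error exceeds the true one by about 0 to 5% up to ICC 0.10, and by about 5 to 6% at ICC 0.20 (for example 0.3045 / 0.2864 = 1.06).

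**4. Sensitivity to the assumptions.** The effect is larger if nobody is lost: with 72 randomised and all analysed, type I error is 4.0% at ICC 0.10 and 3.5% at ICC 0.20. It shrinks with larger blocks: with blocks of 8, type I error at ICC 0.10 is 4.9%. The planned 30% loss weakens balance within sites, so the table in step 3 is the fairer guide.

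**5. Validity of the random-site model.** Its type I error in these runs was 4.6 to 5.9%, with simulation error of about 0.4 points. The upper end is a reason to use small-sample degrees of freedom.

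**The case against.** The strongest reply is that this belongs in the SAP, which is not at hand. Section 8.2 gives age and gender only as examples, so a reader who infers that site and time since onset are excluded goes too far. That part of the reply stands. What remains is that the protocol itself names an unadjusted test for the primary comparison and gives confounding as the reason for the model. An SAP that moved to an adjusted primary analysis would depart from that text.

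Other stronger readings are tempting and also fail:

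- **That the standard errors are wrong in a way that threatens the result.** The error is in the conservative direction, is about 6% at most over the assumed ICC range, and is nil if sites do not differ.
- **That the added precision is free.** This is not true of 15 fixed site terms with about 5 analysed patients each, which cost roughly 1 to 4 points of power unless the ICC exceeds about 0.10 to 0.20. A random effect cost essentially nothing in the runs at ICC 0.
- **That time since onset is known to be more prognostic than age or gender.** The documents contain nothing on this. Onset is also recorded as a date, which is coarse against an outcome in hours. It is a reasonable candidate, not an established predictor.
- **That a time-to-event model is needed.** Nothing in this point requires one, and it would replace the mean difference on which the trial was powered.

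**Conclusion.** The point holds in a modest form. The primary comparison as stated does not use the only stratification factor, the rationale for the adjusted model is misdescribed, and two recorded variables that could sharpen the estimate are not named.

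For an ICC of 0.10 to 0.20, the cost is a type I error of about 4 to 4.5% instead of 5%, and about 1 to 3 points of power. Time since onset could add about 1.4 to 5.3 points (91.0 − 89.6 to 94.9 − 89.6) if it explains 5 to 20% of the variance. The ICC, the R² and the block size are all assumptions. If neither site nor onset time is prognostic, there is little or nothing to gain.

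False positives are not inflated by the stated test, and the 36, 52 and 104 of section 8.1 are unaffected.

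**What to change.** In section 8.2, make one pre-specified adjusted model the primary comparison. It should contain:

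- treatment;
- site as a random effect, not as 15 fixed terms;
- days from onset of diarrhoea to randomisation;
- age and gender if wanted, fixed in advance.

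A linear mixed model with small-sample degrees of freedom would serve and keeps the mean difference of section 8.1. Report the treatment effect with its 95% CI. Replace confounding with prognostic as the reason for the covariates. The unadjusted test can stay as a supporting analysis.

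The cost is a change of wording in the protocol and any SAP, plus slightly more analysis work. No new data are needed, because site and onset date are already recorded.
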